4.5.6. Completers

The completers population is defined as all eligible subjects who completed all phases of the trial without any major protocol deviations.

4.6. General Statistical Considerations

Continuous data, where applicable, will be described using descriptive statistics (i.e. n, mean, standard deviation, median, minimum, and maximum). Categorical data will be described using the subject count and percentage in each category. For the summary statistics of all numerical variables unless otherwise specified, minimum and maximum will be displayed to the same level of precision as reported. Mean and median will be displayed to one level of precision greater than the data collected. Standard deviation / standard error will be displayed to two levels of precision greater than the data collected. P-values will be rounded to three decimal places. If a p-value is less than 0.001 it will be reported as “<0.001.” If a p-value is greater than 0.999 it will be reported as “>0.999.” Data will be displayed in all listings sorted by subject identifier.

Subjects will be identified in the listings by the subject identification number concatenated with the investigator number.

When count data are presented, the percentage will be suppressed when the count is zero to draw attention to the non-zero counts. A row denoted “Missing” will be included in count tabulations where specified on the shells to account for dropouts and missing values. The denominator for all percentages will be the number of subjects in that treatment within the analysis set of interest, unless otherwise specified.

Unless otherwise specified, baseline will be defined as the last non-missing evaluation prior to the first dose of treatment (any of the Ad-RTS-hIL-12, veledimex and cemiplimab) is taken. The study day will be calculated as assessment date - first dose date + 1.

All analyses will be conducted using SAS Version 9.4 or higher.

All data are summarized based on the visit name collected on the CRF page.

4.7. Data Presentation Conventions

The presentation of summary statistics and the conventions for preparing data listings for combining the data for all treated FAS subjects (n=40) are described along the lines of what follows:

- Unless otherwise specified, baseline is the last observation before the first study drug administration. (See section on data handling conventions for more details.) The baseline lesion assessment is considered within 72 hours following Ad-RTS-hIL-12 injection.
- Unless otherwise specified, percentages will be calculated based on the number of patients based on non-missing data as the denominator.
 - A missing values category will also be defined to ensure all subjects are accounted for in prespecified populations for analyses.
 - In analyses presented over time by visit, no imputations will be performed on missing data. All analyses will be based on the observed data.
 - The effective sample sizes at each assessment visit will be based on the total number of subjects with non-missing data for the parameter of interest at that visit.
 - When applicable, additional derived variables will be created based on specifications with or without protocol deviations and violations to assess the comparability and the influence of such deviations. Summary statistics will be provided for continuous variables (e.g., age).
 - Unless otherwise stated, this will consist of the number of subjects with a non-missing value of the variable (n), mean, standard deviation, median, minimum and maximum.
 - The same number of decimal places as in the raw data will be presented when reporting the minimum and the maximum summary statistics,
 - One more decimal place than in the raw data will be presented when reporting the mean, and the median.

- Two more decimal places than in the raw data will be presented when reporting the standard deviation.
- Frequency counts will be provided for categorical variables (e.g., gender).
 - Unless otherwise stated, this will consist of the number of subjects with a response in a particular category and the percentage of the total number of subjects in that column.
 - Unless otherwise stated, categories for missing responses will be included in both the display and in the calculation of percentages (i.e., they will be included in the denominator).
 - Percentages will be rounded to one decimal place.
 - Percents equal to 100 will be presented as 100% and percents will not be presented for zero frequencies.

4.7.1. Overview of Statistical Summaries by Defined Populations

Subject populations will be evaluated and used for presentation and analysis of the following:

- The FAS will be used for summaries of subject disposition, baseline characteristics and for safety. In addition, the FAS will be used in secondary analyses of OS, ORR, and PFS.
- The PP population is to be used for the primary analysis of OS, ORR, PFS and OS.
- When applicable the ESP will be used for analysis of dose limiting toxicities.
- [REDACTED]

4.7.2. Protocol Deviations

A protocol deviation is any change, divergence, or departure from the study design or procedures defined in the protocol. Important protocol deviations are a subset of protocol deviations that may significantly impact the completeness, accuracy, and/or reliability of the study data or that may significantly affect a subject's rights, safety, or well-being. In general, no subject was planned to be removed from any analysis population because of a protocol deviation.

In accordance with ICH E3, patient eligibility violations and important post- treatment protocol deviations will be identified and listed by patient and study center. Major deviations that are considered to potentially impact the efficacy or safety analyses will be tabulated. Important protocol deviations will be identified prior to database lock. Protocol deviations will be listed and summarized by type.

- Deviation from inclusion/exclusion criteria.
- Withdrawal criteria met during the study, but subject was not withdrawn.
- Prohibited concomitant medications.
- Treatment deviation.
- Other protocol deviation.

All protocol deviations will be categorized as either major or minor. The list of protocol deviations along with whether the deviation is classified denoting a major or minor categorization will be finalized prior to database lock.

Major protocol deviations will be presented in a summary table by protocol deviation category for the FAS. Protocol deviations will be presented in a listing.

4.7.3. Relevant Protocol Deviations (RPD)

Originally, relevant deviations from the study protocol were to be documented and accounted for in presenting the data listings and descriptive statistical analyses. Any changes from planned protocol-specified analyses were to be defined in the SAP and reported in the CSR. Instead, protocol deviations will not be produced by Biostatistics. Instead, protocol deviations will be described with an in-text table as applicable in the final CSR. The relevant protocol deviations are described in the [Table 2](#) below.

Table 2: List of Relevant Protocol Deviations

Number	RPD Criteria
1	Poor treatment compliance for either cemiplimab or veledimex (less than 80% of expected total dose of either treatment)
2	Taking prohibited concomitant medication including CYP3A4 inhibitor
3	Others

5. SUBJECT DISPOSITION

5.1. Disposition: Subjects Screened and not treated with any experimental study treatment

[figure not shown]
Subjects screened for study eligibility for whom experimental study treatment was not received regardless of the reason will be denoted as Screen Failures. The number of subjects screened and not treated is reported as part of the subject disposition and nowhere else. These subjects are not included in any study listings or analyses and are not part of the study population for whom the results of the study are reported.

5.2. Disposition: The FAS Population

After displaying the number of subjects screened and not treated, the subject disposition presents the number of subjects in the FAS population as the starting point. All percentages will be based on the number of FAS subjects. Subsequently the table illustrates:

- The number and percent of subjects who:
 - Complete the study,
 - Discontinue from the study by reason for treatment discontinuation and study discontinuation.
- Subjects who discontinued from veledimex.
- Subjects who discontinued from cemiplimab.
- The number and percentage of subjects in each analysis population:
 - PP population and
█ ██████████.
 - If applicable, important protocol deviations will be summarized and listed.
 - Patients could be excluded from the PP population for more than one reason.

Figure 1: Patient Disposition for Protocol Defined Populations

6. DEMOGRAPHICS AND BASELINE CHARACTERISTICS

6.1. Demographics

A summary of demographics and baseline information will be presented. The demographic characteristics consist of age (years), sex, race, and ethnicity. The baseline characteristics consist of baseline height (cm) and baseline body mass index (BMI) (kg/m²). Body mass index is calculated as (body weight in kilograms)/(height in meters)².

Age (years), baseline height (unit), and baseline BMI (kg/m²) will be summarized using descriptive statistics. The number and percentage of sex (Male, Female), race (White, African American, Asian, American Indian or Alaska Native, Native Hawaiian or Other Pacific Islander, Unknown and Other) and ethnicity (Hispanic or Latino, Not Hispanic or Latino and Unknown), will also be reported. Percentages will be based on the total number of subjects in the FAS.

Age is taken to be the subject's age on the date of the Screening visit. Conversions for height and weight are as follows:

- Height (cm) = Height (inches) x 2.54
- Weight (kg) = Weight (lb) x 0.454

Demographics will be listed and tabulated using descriptive statistics.

Subject demographic and baseline characteristics will be presented in a listing.

6.2. Baseline Disease Characteristics

Subject's baseline disease characteristics will be summarized according to the conventions described previously for descriptive statistics of continuous and categorical variables. In addition, baseline characteristics will be transformed into subject characteristic grouping variables for further exploration of the FAS illustrated below.

- Age category

<65 vs \geq 65

- Gender

Female vs Male

- MGMT

unmethylated vs methylated

- Hispanic or Latino

yes =1 vs no=0

- Race

White vs not White

- IDH

wild-type vs mutated

- Prior Steroid use > four weeks before day -7

yes=1 vs no=0

- Enhanced Lesion

unifocal vs Multifocal

- Number of Lesions at Entry

1 vs > 1

- KPS Screening, N(%)

≥70 to 90 vs ≥90

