8.2.1. Assumption Testing

No assumption check is planned for the Kaplan-Meier method.

Patient Characteristic Subgroup Factors

Among the patient factors to be explored are the following patient derived variables.

Age category

- <65 vs ≥ 65

Gender

- Female vs Male

MGMT

- unmethylated vs methylated

Hispanic or Latino

- yes=1 vs no=0

Race

- White vs not White

IDH

- wild-type vs mutated

Prior Steroid

- yes=1 vs no=0

Enhanced Lesion

- unifocal vs Multifocal

Number of Lesions at Entry

- 1 vs > 1

KPS Screening, N (%)

- ≥ 70 to 90 vs ≥ 90

veledimex Dosing Compliance

- $<100\% (<80\%)$ vs $100\% (\geq 80\%)$

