8.4. Other Efficacy Endpoints: Karnofsky Performance Status (KPS)

The KPS measures the ability of cancer subjects to perform ordinary tasks. Scores range from 0 to 100 with a higher score meaning that the patient is better able to carry out daily activities. The KPS is used to determine a patient's prognosis and to measure changes in a patient's ability to function. Subjects must have a KPS score of ≥ 70 at the Screening Visit to be eligible to participate in the study.

KPS measures were planned to be taken at screening, Day -7, Day 0, Day 14, Day 36 and every 3 weeks thereafter. KPS observed values will be provided in listings. Originally planned, changes from baseline at each scheduled visit were to be performed to summarize descriptive statistics. See other efficacy variables under Section 10 describing the changes to the planned analysis.

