Table 14.2.1.1	Objective Response Rate	Per Protocol Population	ORR					
Table 14.2.1.2	95% Confidence Intervals for Overall Response	Per Protocol Population	ORRci					
Table 14.2.2	Progression Free Survival	Per Protocol Population	PFS					
Table 14.2.3	Time to Overall Survival in Months	Per Protocol Population	OS			SS	ADTTE	
Table 14.2.3.1	OS for 20mg group 1 main study and 20 mg expansion for patients characteristics subgroups	Per Protocol Population	OSCAT					

Table 14.3.1.1	Overall TEAEs Summary	Full Analysis Population	AEoverall			AE	ADAE	AeOverall is done
Table 14.3.1.2	Treatment Emergent Adverse Events by System Organ Class and Preferred Term	Full Analysis Population	AEs			AE	ADAE	AEs tables are done
Table 14.3.1.3	Treatment-Related Adverse Events by System Organ Class and Preferred Term	Full Analysis Population	AEs			AE	ADAE	AEs tables are done
Table 14.3.1.4	Adverse Events Leading to Study Discontinuation by System Organ Class and Preferred Term	Full Analysis Population	AEs			AE	ADAE	AEs tables are done
Table 14.3.1.5	Adverse Events Leading to Discontinuation of Study Medication by System Organ Class and Preferred Term	Full Analysis Population	AEs			AE	ADAE	AEs tables are done
Table 14.3.1.6	Adverse Events Leading to Interruption of Study Medication by System Organ Class and Preferred Term	Full Analysis Population	AEs			AE	ADAE	AEs tables are done
Table 14.3.1.7	Adverse Events Leading to Dose Reduction of Study Medication by System Organ Class and Preferred Term	Full Analysis Population	AEs			AE	ADAE	AEs tables are done

Table 14.3.1.8	Adverse Events Leading to Death by System Organ Class and Preferred Term	Full Analysis Population	AEs			AE	ADAE	AEs tables are done
Table 14.3.1.9	Treatment Emergent Adverse Events by System Organ Class, Preferred Term and Severity	Full Analysis Population	AEs			AE	ADAE	AEs tables are done
Table 14.3.1.10	Treatment Emergent Adverse Events by System Organ Class, Preferred Term and Severity with CTCAE Toxicity Grade ≥ 3	Full Analysis Population	AESev			AE	ADAE	AESev tables are done
Table 14.3.1.11	Serious Adverse Events by System Organ Class and Preferred Term	Full Analysis Population	AESev			AE	ADAE	AESev tables are done
Table 14.3.1.12	Treatment Emergent Adverse Events by Preferred Term in Decreasing Frequency	Full Analysis Population	AEPT			AE	ADAE	AEPT tables are done

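### The two screening KPS levels in the SAP both include a score of 90, so this exploratory factor is not disjoint as defined (minor).

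*SAP*

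**What the plan says.** SAP 6.2 states that "baseline characteristics will be transformed into subject characteristic grouping variables for further exploration of the FAS", and gives the KPS grouping as "≥70 to 90 vs ≥90".

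The list headed Patient Characteristic Subgroup Factors, which in the visible text follows SAP 8.2.1 within the OS section, opens with "Among the patient factors to be explored are the following patient derived variables". Its entry for "KPS Screening" is "≥ 70 to 90 vs ≥ 90". The limits are the same as in 6.2.

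SAP 8.4 describes the scale: "Scores range from 0 to 100 with a higher score meaning that the patient is better able to carry out daily activities". It also gives the entry requirement: "Subjects must have a KPS score of ≥ 70 at the Screening Visit to be eligible to participate in the study".

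The output list in the SAP appendices contains Table 14.2.3.1, on the Per Protocol Population, titled in the revised list "OS for 20mg group 1 main study and 20 mg expansion for patients characteristics subgroups". It also contains a forest plot (Figure 14.2.7, same population) with no factors named. The tracking column of the revised list marks the baseline characteristics table (Table 14.1.3.2) as done. Table 14.2.3.1 carries no such mark.

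**The concern.** A grouping variable should place each subject in exactly one level. Here the lower level runs up to 90 and the upper level starts at 90, with nothing to show that the lower level stops short of it. A subject scoring 90 qualifies for both.

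Two outputs are exposed. In the baseline summary, the level counts and percentages would not add up to the column total if anyone scored 90. In an OS summary by KPS, the same subject would contribute to both survival estimates, or would go to whichever level the programmer chose without the SAP recording the choice. Performance status is one of the listed OS subgroup factors, and 90 lies inside the eligible range, so where it falls can change the membership of both levels.

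**Working it through.** There is no stated figure to reproduce: the point concerns a category definition, not a sample size or error rate.

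**Inputs**
- Lower level: 70 ≤ KPS ≤ 90, read literally (SAP 6.2 and the 8.2 factor list).
- Upper level: KPS ≥ 90 (same places).
- Eligible range: 70 to 100 (SAP 8.4; protocol 9.1, inclusion criterion 7).
- FAS size: N = 40 (SAP 4.4).
- Planned number evaluable for efficacy: about 25 (protocol 16.2; SAP 4.1). This stands in for the Per Protocol Population, whose actual size is not given in the visible text.
- Number with screening KPS of exactly 90: m, not given. It is taken as 0 to half of N by assumption.

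**Step 1: which scores meet both conditions.** Every whole-number score from 70 to 100 was checked. Only 90 meets both. The table shows selected scores. The result does not depend on KPS being scored in steps of ten, which the documents do not state.

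| KPS | As written | ≥70 to <90 vs ≥90 | ≥70 to 90 vs >90 |
|---|---|---|---|
| 70 | lower | lower | lower |
| 80 | lower | lower | lower |
| 90 | **both** | upper | lower |
| 100 | upper | upper | upper |

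Either disjoint split puts each score in one level. The two splits differ only in where 90 goes, so moving from one to the other shifts exactly m subjects.

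**Step 2: size of the overlap.** Each subject at 90 is counted twice, so the level counts sum to N + m and the percentages to 100 × (N + m)/N.

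| N = 40: m | Sum of level counts | Sum of percentages |
|---|---|---|
| 0 | 40 | 100% |
| 4 | 44 | 110% |
| 10 | 50 | 125% |
| 16 | 56 | 140% |
| 20 | 60 | 150% |

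For N = 25, assumed values of m = 0, 2, 6, 10 and 12 give 100%, 108%, 124%, 140% and 148%.

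**Step 3: is it resolved elsewhere?** Other factors in the same lists are cut cleanly: age is <65 vs ≥65, and number of lesions is 1 vs >1. The visible part of SAP 10.2 drops parametric OS, fixed-time OS rates, PFS, ORR, tumor response rate and best overall response. It does not mention OS by patient characteristics, although part of Section 10 is redacted. The SAP contents list also shows a section 8.2.2 on exploratory OS analyses whose heading does not appear in the visible body. Nothing that can be read settles the boundary.

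**The case against.** The best defence is that this is a drafting slip with an obvious intention. The only explicit comparison sign attached to 90 is in the upper level, and the lower level's upper end carries no sign at all. That favours placing 90 in the upper level. A derived grouping variable would also normally give each subject a single value, so double counting may never happen in the programmed output. Both arguments have force. They make an undocumented boundary more likely in practice than literal double counting, but they do not make the written definition disjoint. The other split, 70 to 90 vs above 90, is less natural but is not excluded.

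A reader might infer more than the documents support:

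- **That subjects fall in both arms of an invalid comparison.** The trial is single-arm, so these are levels of one factor. SAP Section 8 plans no formal hypothesis test for the primary and secondary endpoints, and 6.2 and 8.2 present these factors for exploration only.
- **That the forest plot is affected.** Figure 14.2.7 names no factors and its shell is not in the documents. KPS as a row is an inference from the factor list.
- **That the cut could be chosen after seeing OS by KPS.** The SAP reports 40 treated subjects and the baseline table is marked done, so data were in hand. The documents do not show that anyone had seen OS by KPS. If the finished baseline table includes KPS, a split has already been coded.
- **That a particular number of subjects is affected.** A third of 40 would be about 13, but the proportion scoring 90 is not reported and the OS subgroup table uses the Per Protocol Population, not the FAS.

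The title of Table 14.2.3.1 also refers to a main-study group and an expansion group that do not match this single-cohort design, so how the table would be run here is uncertain.

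**Conclusion.** The definition is wrong as written, and the matter is minor. A screening KPS of 90 satisfies both levels in SAP 6.2 and in the 8.2 factor list, and no visible text resolves it. The baseline grouping and any OS-by-KPS estimate in Table 14.2.3.1 are therefore not disjoint as defined.

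The practical size depends wholly on m. If nobody scored 90 there is no effect; if half the FAS did, the percentages sum to 150%. That range is an assumption, not a finding about the data. The primary OS estimate, which is Kaplan-Meier on the Per Protocol Population without KPS, is unaffected. The conclusion also assumes that the redacted and non-visible parts of Sections 8 and 10 neither define the cut nor drop the OS subgroup work.

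**What to change.** In SAP 6.2 and in the Patient Characteristic Subgroup Factors list, write the KPS levels as ≥70 to <90 vs ≥90. This adds one symbol in each place, keeps the explicit lower limit of the upper level, and follows the pattern of the age split.

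Then check the code behind Table 14.1.3.2, if that table shows grouped KPS, along with Table 14.2.3.1 and Figure 14.2.7 if it has a KPS row, and confirm that all use the same split. If a different split was coded, those outputs need a rerun. That is the only cost.

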6.3. Alcohol, Tobacco and Caffeine Usage

Not Applicable

6.4. Medical History

6.4.1. General Medical History

Medical history will be coded using the Medical Dictionary for Regulatory Activities (MedDRA) Version 23.0. The number and percentage of subjects with any medical history will be summarized overall and for each system organ class and preferred term. Percentages will be calculated based on number of subjects in the FAS.

Subject medical history data including specific details will be presented in a listing.

6.4.2. Disease-Specific History

Disease specific history will consist of initial disease status, grade at initial diagnosis, initial MGMT gene promoter status and initial IDH status. Disease specific history will be summarized by frequency count and percentage based on FAS population.

Subject disease-specific history data including specific details will be presented in a listing.

7. TREATMENTS AND MEDICATIONS

7.1. Prior and Concomitant Medications

Verbatim terms on case report forms will be mapped to Anatomical/Therapeutic/Chemical (ATC) class and Generic Drug Names using the World Health Organization Drug Dictionary (WHO-DD V5).

- Prior medications are defined as medications with a stop date occurring before the first dose of treatment (any of the Ad-RTS-hIL-12, veledimex and cemiplimab) is taken.
- Concomitant medications are those medications taken after the initial dose of study drug. Concomitant medications are defined as medications that are ongoing on the first dose date, or with a start date missing or occurring on or after the first dose date.
- Concomitant medications, including blood products, vitamins, and other supplements received during the screening period (28 days) prior to initiating study treatment will be recorded. Concomitant medications will continue to be collected through 90 days after the subject's last dose of any study drug.

For inclusion in prior and/or concomitant medication tables, incomplete medication start and stop dates will be imputed as follows:

Missing start dates (where UK, UKN and UNKN indicate unknown or missing day, month and year respectively):

- UK-MMM-YYYY: If the month and year are different from the month and year of the first dose of study drug, assume 01-MMM-YYYY. If the month and year are the same as the first dose of study drug month and year and the end date (after any imputation) is on or after the first dose of study drug, then assume the date of the first dose of study drug. If the month and year are the same as the first dose of study drug month and year and the end date (after any imputation) is prior to the first dose of study drug, then assume the end date for the start date.
- DD-UKN-YYYY/UK-UKN-YYYY: If the year is different from the year of the first dose of study drug, assume 01-JAN-YYYY of the collected year. If the year is the same as the first dose of study drug year and the end date (after any imputation) is on or after the first dose of study drug, then assume the date of the first dose of study drug. If the year is the same as the first dose of study drug and the end date (after any imputation) is prior to the first dose of study drug, then assume the end date for the start date.

Missing stop dates (where UK, UKN and UNKN indicate unknown or missing day, month and year respectively):

- UK-MMM-YYYY: Assume the last day of the month.
- DD-UKN-YYYY/UK-UKN-YYYY: Assume 31-DEC-YYYY.

If start date is completely missing and end date is not prior to the first dose, then the medication will be classified as both prior and concomitant. If the start date is completely missing and the

end date is within 28 days prior to the first dose of study drug, then the medication will be classified as prior. If the end date is missing, then the medication will be classified as ongoing. Medications for which the start and end dates are missing will be classified as prior and concomitant.

